 Mount Sinai	Protocol Name:	A double-blinded, placebo-controlled study to evaluate the tolerability and efficacy of Enstilar® (calcipotriene and betamethasone dipropionate) Foam in the treatment of chronic plaque psoriasis in patients with skin of color (Fitzpatrick skin phototypes IV-VI).
	Principal Investigator:	[name], MPH
	Primary Contact Name/Contact Info:	[name], MPH [contact]
	Date Revised:	08/10/2017
	Study Number:	IF2166478

1. Provide written, signed and dated informed consent prior to initiating any study-related activities.
2. Male or female >18 years of age at the time of screening
3. Fitzpatrick Skin phototype IV-VI, non-white race/ethnicity, including but not limited to African Americans, Asians, Pacific Islanders and Hispanics.
4. Clinical diagnosis of chronic plaque-type psoriasis of the body
5. Plaque psoriasis with $\geq 2\%$ Body Surface Area (BSA) involvement (may include scalp involvement), PASI Score ≥ 2 , IGA mod 2011 score of 2 or greater (based on scale of 0-4)
6. Females of childbearing potential (FCBP) must have a negative pregnancy test at Screening and Baseline. While using investigational product and for at least 28 days after last application of investigational product, FCBP who engage in activity in which conception is possible must use one of the approved contraceptive options described below:

Option 1: Any one of the following highly effective methods: hormonal contraception (oral, injection, implant, transdermal patch, vaginal ring); intrauterine device (IUD); tubal ligation; or partner's vasectomy;

OR

Option 2: Male or female condom (latex condom or nonlatex condom NOT made out of natural [animal] membrane [for example, polyurethane]; PLUS one additional barrier method: (a) diaphragm with spermicide; (b) cervical cap with spermicide; or (c) contraceptive sponge with spermicide.
7. Must be in general good health as judged by the Investigator, based on medical history and physical examination. (NOTE: The definition of good health means a subject does not have uncontrolled significant co-morbid conditions).

Exclusion:

1. Form of diagnosed psoriasis other than chronic plaque psoriasis (i.e. guttate, erythrodermic, pustular)
2. Diagnosis of other active, ongoing skin diseases or skin infections that may interfere with examination of psoriasis lesions

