Urine Pregnancy Test		X	X				
BSA		X	X		X	X	X
Investigator IGA mod 2011 score (and ScIGA if applicable)		X	X		X	X	X
PASI score (PSSI if applicable)		X	X		X	X	X
Mexameter measurement of erythema and melanin indices			X		X	X	X
Investigator dyspigmentation VAS			X			X	X
Patient Global Assessment of severity (PaGA)			X		X	X	X
Patient pruritus VAS			X	X	X	X	X
Patient dyspigmentation VAS			X			X	X
Dermatology Life Quality Index (DLQI)			X		X	X	X
Local Tolerability Assessment			X	X	X	X	X
Treatment satisfaction evaluation					X	X	X
Study Drug Training			X				
Study Drug Dispensation and Return			X			X	X

 Mount Sinai	Protocol Name:	A double-blinded, placebo-controlled study to evaluate the tolerability and efficacy of Enstilar® (calcipotriene and betamethasone dipropionate) Foam in the treatment of chronic plaque psoriasis in patients with skin of color (Fitzpatrick skin phototypes IV-VI).
	Principal Investigator:	[name], MPH
	Primary Contact Name/Contact Info:	[name], MPH [contact]
	Date Revised:	08/10/2017
	Study Number:	IF2166478

This is a single-center study and will consist of 3 phases. Phase 1 - screening phase, Phase 2 - Double-blinded, vehicle-controlled phase, and Phase 3 - Open-label and maintenance phase

Phase 1 - The screening phase will last up to 28 days. Screening and baseline may occur on the same day if subject does not require a wash-out period.

Phase 2 - double-blinded, placebo-controlled phase to evaluate the tolerability and efficacy of Enstilar® (calcipotriene and betamethasone dipropionate) Foam versus placebo in the treatment of chronic plaque psoriasis in patients with skin of color (Fitzpatrick skin phototypes IV-VI). This phase will last 4 weeks (baseline to week 4). Subjects will be randomized in a 4:1 ratio to Enstilar® or placebo, respectively. The study product will be applied once daily for 4 weeks.

Phase 3 - Open-label and maintenance phase. Subjects who were randomized to placebo during phase 2 will receive Enstilar daily x 4 weeks. Subjects who were randomized to Enstilar during phase 2 will switch to Enstilar twice weekly x 4 weeks as maintenance treatment.

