During phase 2 of the study, the study product (Enstilar ® foam or vehicle) should be applied topically to affected areas of the skin once daily. During phase 3, frequency of Enstilar ® is dependent on treatment group. Those randomized to Enstilar ® during phase 2 will start a maintenance regimen: twice weekly application of Enstilar ® for 4 weeks. Those randomized to vehicle during phase 2 will start the treatment regimen: once daily application of Enstilar ® for 4 weeks.

The procedures and assessment performed during this study are described in detail below:

Informed Consent: Prior to the start of the study, potential subjects will be given an IRB-approved Informed Consent Document (ICD) containing a Health Insurance Portability and Accountability Act (HIPAA) disclosure agreement to read, understand, and sign. All questions about the study should be answered to the satisfaction of the candidate subject. They will have all of their study-related questions answered by the PI or designee, and if they agree to participate, the subject will sign the ICD. The subjects will retain one original copy and one photocopy will be kept in the study file. The subjects who sign an ICD will be assigned a screening number.

Demographics: Subjects will be asked to complete a questionnaire about their demographics at the screening visit. This will include date of birth, sex, race, and ethnicity.

Eligibility Assessment (Inclusion/Exclusion): After providing informed consent, subjects will be assessed for study eligibility at the Screening visit, which includes limited physical examination, skin type assessment, vital signs, height and weight, investigator severity ratings (PASI, PGA, PSSI and PScIGA if applicable), review of medical history and concomitant medications as well as prior medications/treatments, and urine pregnancy test (if applicable). These assessments will be described below. The PI or a medically qualified designee must review this information (i.e. medical history, concomitant medication, and eligibility review) for each subject to confirm their eligibility before enrollment. Eligibility will be assessed at Screening and Baseline visits.

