Dermatology Life Quality Index (DLQI): DLQI is a validated 10-question questionnaire developed to address quality of life in patients with dermatological disorders. It has previously been used with success to assess the impact of psoriasis on quality of life. Patients will be asked to fill out a DLQI at baseline, week 2, week 4, and week 8.

Patient Satisfaction Questionnaire: Subjects will be asked to complete a questionnaire asking about satisfaction with the study product, including satisfaction with the product vehicle, ease of application, and overall satisfaction with the treatment product.

Local Tolerability Assessment: Assessment of local safety and tolerability will be completed at baseline and weeks 1, 2, 4, and 8. The investigator or designated site staff will assess for: perilesional erythema, edema, dryness, and erosion. These parameters will be graded on a scale of 0 (absent) to 3 (severe). The subjects will also be asked about application site burning and pain after application of the study drug. Subjects will be asked to grade their burning/stinging from 0 (absent) to 3 (severe). Only severe site reactions or reactions that require discontinuation of the study product will be recorded as AEs.

 Mount Sinai	Protocol Name:	A double-blinded, placebo-controlled study to evaluate the tolerability and efficacy of Enstilar® (calcipotriene and betamethasone dipropionate) Foam in the treatment of chronic plaque psoriasis in patients with skin of color (Fitzpatrick skin phototypes IV-VI).
	Principal Investigator:	[name], MPH
	Primary Contact Name/Contact Info:	[name], MPH [contact]
	Date Revised:	08/10/2017
	Study Number:	IF2166478

Urine Pregnancy test: Urine pregnancy test will be performed at screening and baseline visits for women of child-bearing potential. A woman is considered post-menopausal if she has not had a menstrual period in >12 months.

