- **Allergic contact dermatitis** – Topical calcipotriene and topical corticosteroids have both been associated with allergic contact dermatitis.
- **Risk of ultraviolet light exposure** – patients would have using Enstilar® foam should avoid excessive exposure to natural and artificial sunlight (i.e. tanning booths, sun lamps)
- **Flammability** – The propellants in Enstilar® foam are flammable. Subjects should avoid smoking, flames, and fire during and immediately following Enstilar® application.

Enstilar® foam is designated as pregnancy category C, meaning that there are no adequate and well controlled studies in pregnant women. Studies of calcipotriene administered orally in rats and rabbits have demonstrated increased maternal and fetal toxicity at doses above 144 mcg/m²/day (rabbits) and skeletal abnormalities at dosages above 432 mcg/m²/day in rabbits and 324 mcg/m² /day in rats. These are lower than the estimated maximum topical dose of calcipotriene in humans (460mcg/m²/day).

 Mount Sinai	Protocol Name:	A double-blinded, placebo-controlled study to evaluate the tolerability and efficacy of Enstilar® (calcipotriene and betamethasone dipropionate) Foam in the treatment of chronic plaque psoriasis in patients with skin of color (Fitzpatrick skin phototypes IV-VI).
	Principal Investigator:	[name], MPH
	Primary Contact Name/Contact Info:	[name], MPH [contact]
	Date Revised:	08/10/2017
	Study Number:	IF2166478

Betamethasone propionate has been shown to be teratogenic in mice and rabbits when given subcutaneously at dosages of 468 mcg/m² /day (mice) and 30 mcg/m² /day (rabbits). Again, these levels are lower than the estimated maximum topical dose in humans (~5,950mcg/m²/day).

When administered systemically, corticosteroids have been shown to enter human milk and can have negative effects on infant health. Possible risks of systemic corticosteroids on infants include growth suppression and altered production of endogenous steroids. It is not known whether topically administered calcipotriene and/or corticosteroids results in sufficient systemic absorption to produce detectable quantities of these medications in human milk. Enstilar®, therefore, should not be used by women while breastfeeding.

3) Provisions for Research Related Harm/Injury

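### The only scheduled pregnancy tests are at Screening and Baseline, so the vehicle arm starts Enstilar at Week 4 on a test 23 to 33 days old, and none is scheduled at end of treatment

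*Protocol*

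**What the plan says.** Three places in the protocol set the timing of the test, and they agree.

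- Inclusion criterion 6: females of childbearing potential "must have a negative pregnancy test at Screening and Baseline".
- Table 1 (Assessment Schedule): the row "Urine Pregnancy Test" is marked at Visits 1 and 2 and blank at Visits 3 to 6 (Weeks 1, 2, 4 and 8).
- Urine Pregnancy test paragraph under Procedures Involved in the Human Research: "Urine pregnancy test will be performed at screening and baseline visits for women of child-bearing potential".

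The description of Phase 1 adds: "Screening and baseline may occur on the same day if subject does not require a wash-out period". For such a subject both tests fall on one day.

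Product is dispensed at Baseline and at Week 4. On the vehicle arm the Phase 3 text reads: "Subjects who were randomized to placebo during phase 2 will receive Enstilar daily x 4 weeks". The later description of product use agrees: "Those randomized to vehicle during phase 2 will start the treatment regimen: once daily application of Enstilar". The Enstilar arm changes at Week 4 from once-daily to twice-weekly application for a further four weeks. A subject who stops early is asked to attend for the Visit 6 procedures, which include no pregnancy test.

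Pregnant women are excluded (exclusion criterion 5; Vulnerable Populations). Contraception is required "While using investigational product and for at least 28 days after last application of investigational product". The Risks to Subjects section reports pregnancy category C and animal findings of fetal toxicity, skeletal abnormality and teratogenicity. The data management section mentions pregnancy notification forms.

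**The concern.** The protocol treats exposure in pregnancy as something to prevent. It does not rely on contraception alone at entry, because it also asks for negative tests. The tests, however, are tied to study entry and not to the start of active drug. In the Enstilar arm the two coincide. In the vehicle arm they are four weeks apart, because the design moves those subjects to Enstilar at Week 4.

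Two situations are therefore not covered by any scheduled test. A woman who conceives during the vehicle phase could start daily Enstilar with her pregnancy unrecognised. A woman who conceives on Enstilar in the first four weeks could be supplied again at Week 4, and her pregnancy could also go unnoticed at the final visit. What is at stake is protection of subjects and completeness of pregnancy reporting. The efficacy analysis is not affected.

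**Working it through.** The protocol gives no figure of its own to reproduce. The check sets the test schedule against the exposure schedule and counts days from Baseline (day 0).

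**Inputs**
- Last scheduled test: Baseline, day 0 (Table 1).
- Week 4 visit: day 28, window ±5 days (Table 1).
- Week 8 visit: day 56, window ±5 days (Table 1). Study Timelines lists no later visit.
- Contraception: at least 28 days beyond the last application (inclusion criterion 6).
- Planned arm sizes: 20 Enstilar, 5 vehicle.

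**Age of the last test**
1. When vehicle subjects first receive Enstilar, and Enstilar subjects are supplied again: 28 ± 5 = 23 to 33 days.
2. At the final visit: 56 ± 5 = 51 to 61 days.
3. At the end of the minimum contraception period: (56 ± 5) + 28 = 79 to 89 days. This assumes that the last application is at the Week 8 visit.

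**Scheduled tests before and after first contact with Enstilar**

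| | Enstilar arm (20) | Vehicle arm (5) |
|---|---|---|
| First Enstilar | Baseline | Week 4 |
| Age of last test at that point | 0 days | 23 to 33 days |
| Weeks of Enstilar planned | 8 | 4 |
| Scheduled tests after Baseline | 0 | 0 |

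**How many women this might touch.** The protocol does not give the number of women of childbearing potential. As an illustration only, assume that half of the subjects are such women and that contraceptive failure is 1% to 20% per year. Neither figure comes from the protocol.
- Vehicle arm, Weeks 0 to 4: 2.5 × 4/52 = 0.192 woman-years. Expected conceptions are 0.192 × 0.01 = 0.002 to 0.192 × 0.20 = 0.04.
- All 25 subjects, Weeks 0 to 8: 12.5 × 8/52 = 1.92 woman-years. Expected conceptions are 1.92 × 0.01 = 0.02 to 1.92 × 0.20 = 0.38.

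These counts would be zero if no subject were of childbearing potential, and double if all were.

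**The case against.** The strongest case on the other side has four parts.

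*Nothing conflicts.* A reader might infer that the protocol contradicts itself, or that it breaks a rule of its own requiring a negative test before first active drug. Neither is supported. The three places on timing agree, and inclusion criterion 6 is an entry criterion that both arms meet in the same way. A check before first contact with Enstilar is a purpose one can read into the criterion; no passage states it as a rule. This part stands, and it limits the point to a gap in the schedule.

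*Safeguards exist.* Contraception from a defined list is mandatory, and women unwilling to use it are excluded. Staff ask about adverse events and changes in health at Weeks 1, 2, 4 and 8. It would therefore be too strong to say that a pregnancy comes to light only if the subject volunteers it. Part of the safety monitoring plan was also not available for this review, so testing for cause cannot be ruled out. These measures lower the risk. An interview does not verify status, however, and Table 1 settles which tests are scheduled.

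*The animal figures cannot carry the argument.* The risk section says of betamethasone: "Again, these levels are lower than the estimated maximum topical dose in humans". It makes the same comparison for calcipotriene. A reader might turn these doses into safety margins. The animal doses were oral or subcutaneous and the human figure is an estimated topical maximum, so their ratios do not measure relative exposure. They show only that the protocol recognises a reproductive risk.

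*The numbers are small.* Only five subjects, of both sexes, are planned for vehicle, and the illustration puts expected conceptions there well below one. This stands, and it is why the point rests on low cost rather than on frequency.

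**Conclusion.** The point holds as a gap in the assessment schedule. No pregnancy test is scheduled after Baseline. The 5 planned vehicle subjects begin Enstilar 23 to 33 days after their last test, the 20 planned Enstilar subjects are supplied again at Week 4 untested, and the last test is 51 to 61 days old at the Week 8 visit. This fits poorly with the protocol's own exclusion of pregnant women, its entry tests, its contraception requirement and its stated reproductive risk.

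These intervals follow directly from Table 1. The number of women affected is unknown and probably small. A reader might also take all subjects to have eight weeks on Enstilar. That is true of study product, but the vehicle arm has Enstilar for only four of those weeks. The point ranks as a cheap improvement.

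**What to change.** Reconcile the test schedule in inclusion criterion 6, Table 1 and the Urine Pregnancy test paragraph with the Week 4 start of Enstilar in the vehicle arm and with end of treatment, including early termination. The site already runs the urine test, and Visits 5 and 6 already exist, so no new procedure or visit is needed. The sponsor should decide the exact timing and how a result bears on dispensing; this review proposes no rule for either. The amended text should also say how the contraception period after the final visit is covered, since a test at Visit 6 would not reach its end.

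The cost is a protocol amendment, a revised consent document (which needs IRB and sponsor approval), and at most two urine tests per woman of childbearing potential. The ceiling is 25 × 2 = 50 tests if every subject were in that group.

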 Mount Sinai	Protocol Name:	A double-blinded, placebo-controlled study to evaluate the tolerability and efficacy of Enstilar® (calcipotriene and betamethasone dipropionate) Foam in the treatment of chronic plaque psoriasis in patients with skin of color (Fitzpatrick skin phototypes IV-VI).
	Principal Investigator:	[name], MPH
	Primary Contact Name/Contact Info:	[name], MPH [contact]
	Date Revised:	08/10/2017
	Study Number:	IF2166478

3. Ongoing use of other psoriasis treatment including but not limited to topical or systemic corticosteroids, other topical medications (i.e. coal tar), oral or biologic medications for the treatment of psoriasis, and UV therapy. The following washout periods will be required:
 - 2 weeks for topical therapy
 - 2 weeks for phototherapy
 - 12 weeks for biologic or targeted therapies
 - 4 weeks for other systemic therapies
4. Use of oral estrogen therapy, excluding oral contraceptive pills
5. Women who are pregnant, nursing, or of child-bearing potential who are unwilling to use appropriate method(s) of contraception.
6. Patients unwilling to limit exposure to UV light
7. Current significant medical problems that, in the discretion of the investigator, would put the patient at significant risk
8. Patients with disorders of calcium metabolism and/or hypercalcemia.
9. Use of any investigational drug within 4 weeks prior to randomization, or 5 pharmacokinetic/pharmacodynamics half-lives, if known (whichever is longer).
10. History of allergy to any component of the IP

c) Number of Subjects

Patients with skin types IV-VI with chronic plaque-type psoriasis will be screened with a goal of 25 total subjects randomized. All 25 randomized subjects are expected to complete all study procedures. Individuals who provide informed consent and fail to meet all of the inclusion and exclusion criteria during the initial evaluation will be considered a “screening failure.”

d) Study Timelines

The study will consist of 6 visits over up to 12 weeks (up to 4 week screening period plus 8 weeks enrolled in study). Study visits will be conducted at Screening (Visit 1), Baseline (Visit 2, Week 0), Week 1 (Visit 3), Week 2 (Visit 4), Week 4 (Visit 5), and Week 8/discontinuation (Visit 6).

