9. Change in physician dyspigmentation visual analog scale (VAS) at weeks 4 and 8.

An investigator will perform a visual analog scale (VAS) rating the degree of dyspigmentation of the skin. This VAS will range from - 5 to 5 as follows: 5 severe dark

 Mount Sinai	Protocol Name:	A double-blinded, placebo-controlled study to evaluate the tolerability and efficacy of Enstilar® (calcipotriene and betamethasone dipropionate) Foam in the treatment of chronic plaque psoriasis in patients with skin of color (Fitzpatrick skin phototypes IV-VI).
	Principal Investigator:	[name], MPH
	Primary Contact Name/Contact Info:	[name], MPH [contact]
	Date Revised:	08/10/2017
	Study Number:	IF2166478

brown pigmentation (darkest imaginable color), 4 dark brown pigmentation, 3 medium brown pigmentation, 2 light brown pigmentation, 1 slight dark pigmentation (barely perceptible compared to surrounding skin), 0 baseline skin pigmentation, -1 slight hypopigmentation (barely perceptible compared to surrounding skin), -2 mild hypopigmentation (light brown), -3 moderate hypopigmentation (creme-colored skin), -4 severe hypopigmentation (almost complete absence of pigment), -5 depigmentation (complete absence of pigment). This VAS will be performed at baseline and weeks 4 and 8.

10. Change from baseline in Dermatology Life Quality Index (DLQI) total score at weeks 2, 4 and 8.

Subjects will complete a DLQI at baseline, week 2, week 4 and week 8. Change in DLQI total score between baseline and week 4 will be assessed.

 Mount Sinai	Protocol Name:	A double-blinded, placebo-controlled study to evaluate the tolerability and efficacy of Enstilar® (calcipotriene and betamethasone dipropionate) Foam in the treatment of chronic plaque psoriasis in patients with skin of color (Fitzpatrick skin phototypes IV-VI).
	Principal Investigator:	[name], MPH
	Primary Contact Name/Contact Info:	[name], MPH [contact]
	Date Revised:	08/10/2017
	Study Number:	IF2166478

a) Procedures Involved in the Human Research

Table 1: Assessment Schedule

	Visit	1	2	3	4	5	6
	Week	-4 to BL	0 (BL)	1	2	4	8 ET/E OT
	Visit Window (days)			±2	±2	±5	±5
Assessment							
Informed Consent		X					
Demographics		X					
Inclusion/Exclusion		X	X				
Medical History		X					
Psoriasis treatment history		X					
AE/SAE assessment		X	X	X	X	X	X
Concomitant medications		X	X	X	X	X	X
Vital Signs		X					
Height and Weight		X					
Physical Examination		X					
Fitzpatrick Skin Type assessment		X					
Photography			X			X	X

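### The post-menopausal rule rules out no other cause of absent periods, so a woman who can still conceive could go without both entry pregnancy tests

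*Protocol*

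**What the plan says.** Four parts of the protocol bear on this.

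- **Procedures, Urine Pregnancy test.** The test is done at screening and baseline in women of child-bearing potential. The next sentence is: "A woman is considered post-menopausal if she has not had a menstrual period in >12 months". It carries no age limit, no condition on why periods stopped, and no confirmatory test.
- **Inclusion 6.** Females of childbearing potential (FCBP) "must have a negative pregnancy test at Screening and Baseline". Those for whom conception is possible must also use contraception during treatment and "for at least 28 days after last application of investigational product". Option 1 begins with "hormonal contraception (oral, injection, implant, transdermal patch, vaginal ring); intrauterine device (IUD" and goes on to tubal ligation and a partner's vasectomy.
- **Other entry criteria.** Inclusion 2 reads "Male or female >18 years of age at the time of screening", with no upper limit. Exclusion 4 reads "Use of oral estrogen therapy, excluding oral contraceptive pills", so oral contraceptive users may enter. Exclusion 5 bars "Women who are pregnant, nursing, or of child-bearing potential who are unwilling to use appropriate method(s) of contraception".
- **Table 1 and Eligibility Assessment.** The urine test is marked at Visits 1 and 2 only, and the eligibility paragraph asks for it where applicable.

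None of the text shown defines FCBP.

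**The concern.** Three requirements turn on whether a woman is FCBP: the two tests, the contraception rule and Exclusion 5. The only criterion offered for sorting women is the 12-month sentence, and absent periods do not establish menopause. In a trial open to women just over 18, a long gap may come from a medical condition, or from an injection, implant or IUD that Inclusion 6 itself accepts.

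What is at stake is individual safety. Pregnancy is an exclusion, and the two urine tests are the only objective check for it stated at entry. Four in five subjects are assigned active foam in the blinded phase, and everyone who continues is assigned it in the open-label phase. The Risks section says adequate studies in pregnant women are lacking and reports fetal harm in animals. Those animal data come from oral or subcutaneous dosing, so they explain why the safeguard exists but do not estimate risk from topical use.

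**Working it through.** The protocol states no figure on this point, so there is nothing to reproduce. The check is mainly one of reading the provisions together.

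**Step 1: does the sentence work as an exemption?** It does not say so. It directly follows the rule on who is tested, under the same label, and has no other evident use there. Reading it as a test exemption is an inference, but a reasonable one.

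**Step 2: is it qualified elsewhere?** Inclusion 6, Exclusion 5, the eligibility paragraph and Table 1 add no age, cause or confirmation, and none defines FCBP.

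**Step 3: apply both provisions to the women concerned.**

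| Woman with no period for more than 12 months | By the 12-month sentence | By Inclusion 6 | Result |
|---|---|---|---|
| Natural menopause | Post-menopausal | Not FCBP in the ordinary sense | Consistent |
| Hormonal method or IUD | Post-menopausal | FCBP, as implied by Option 1 | Conflict over the tests; contraception continues through the method |
| Medical cause, still able to conceive, no method | Post-menopausal | FCBP in the ordinary sense | Conflict over the tests; contraception in doubt only by further inference |

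**Step 4: size for one misclassified woman.**

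- Tests missed: Screening + Baseline = 1 + 1 = 2 of the 2 planned. The protocol lets these visits fall on the same day when no wash-out is needed.
- Contraception, hormonal or IUD user: 0 days lost while she stays on the method.
- Contraception, no method, and only if the 12-month sentence is also carried over to Inclusion 6: 8 weeks × 7 + 28 = 84 days on schedule. With Visit 6 at the late end of its window ("Visit Window (days" row of Table 1, ±5): 56 + 5 + 28 = 89 days.

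These figures restate the schedule for one woman. They do not measure how often this would occur, and the protocol gives nothing from which to estimate that.

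**The case against.** The strongest reply is that Inclusion 6 governs and a procedural sentence does not override it. A woman who can conceive is of child-bearing potential in the ordinary meaning of the words, so she must have two negative tests and, where relevant, use contraception. The entry criteria never use the term post-menopausal and do not refer to the 12-month sentence. Option 1 shows that FCBP status does not turn on bleeding alone.

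The practical safeguards are also real. Medical history is taken, and current medications and those of the previous month are recorded. Inclusion 7 requires good general health on history and examination. The investigator or a medically qualified designee confirms eligibility, which is assessed at both Screening and Baseline. Asking for the test where applicable leaves room to test anyone in doubt.

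Most of this stands. A reader might infer that the protocol exempts fertile women outright from both testing and contraception. The documents do not support that: the test exemption is inferred from placement, and losing contraception takes a second inference, because that duty rests on Inclusion 6 and Exclusion 5.

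What remains is that the protocol gives the reviewing clinician an explicit rule that is wrong for some women, and nothing shown requires asking why periods stopped. The safeguards make an error unlikely but do not correct the rule.

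**Conclusion.** The point holds as a badly fixed definition of low severity. Applied as the apparent test exemption, the 12-month rule could leave a woman with absent periods from a medical cause, a hormonal method or an IUD untested at both entry visits, in tension with Inclusion 6. The size is at most two tests per affected woman. The 84 to 89 days without a contraception requirement apply only to a woman using no method, and only on the further inference.

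This rests on two assumptions: that the sentence is meant to separate women who are tested from those who are not, and that no definition of FCBP exists outside the text shown. No number of affected women is claimed; with 25 subjects of both sexes and clinician review, it is likely to be very small.

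A reader might also take this as a threat to the trial's results. It is not: endpoints, sample size, randomisation and analysis are untouched. The point concerns who is tested, not how often.

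**What to change.** Make two short edits.

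1. Under Urine Pregnancy test, define post-menopausal as *more than 12 months without a period and with no alternative cause, such as hormonal contraception, an IUD or a medical condition*.
2. In Inclusion 6, state that all other women without documented hysterectomy or bilateral oophorectomy, including Option 1 users, are FCBP and have both urine tests.

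The eligibility form should carry the same wording.

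The cost is the edit plus two urine tests per reclassified woman; some of those tested will prove to be truly post-menopausal. A few women whose medical condition also makes them infertile would come under the contraception rule where conception is considered possible. Visits and analysis do not change.
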